### **6.6.2 Labelling of plasma PK samples**

PK blood sample tubes will be clearly labelled with the study number, patient number, visit number, date and actual time of collection. The date and time of collection will also be recorded on the lab data collection form provided. Any samples collected outside of the acceptable time windows will have an explanatory comment added to the source documents.

Pre-printed labels and sample registration forms will be provided for plasma drug level samples detailing study number, patient number, visit number, actual sample time and date.

A label will be completed and affixed to a plain tube at the time of plasma preparation. Identical data will be recorded on the sample registration form.

It is important that sample registration forms are completed accurately and that each tube can be accurately and easily identified.

### **6.6.3 Determination of drug concentration**

Samples for determination of drug concentration in plasma will be analysed by Covance, Shanghai on behalf AstraZeneca, using a validated, highly sensitive and specific, liquid chromatography mass spectrometry method (LC-MS-MS), using deuterated fulvestrant as the internal standard (IS). Concentration of fulvestrant will be calculated from peak area ratios[fulvestrant/IS] by reference to calibration series constructed by adding known amounts of fulvestrant to control plasma and extracting these standards in parallel with the test samples. Quantification will be by reference to a least squares linear regression line generated from the standard sample.

## **6.7 Pharmacodynamics (Not Applicable)**

## **6.8 Pharmacogenetics (Not Applicable)**

## **6.9 Health economics (Not Applicable)**

# **7. BIOLOGICAL SAMPLING PROCEDURES**

## **7.1 Volume of blood**

The total volume of blood drawn from each patient will depend on the length of time the patient receives study medication. [Table 4](#) is a guide to the approximate volume of blood that will be drawn from each patient, based on the assumption that each patient will receive study treatment for 24 weeks. Actually, when the blood samples are assessed at the local hospital laboratory, necessary volumes of blood samples will be collected at each medical centre.

**Table 4** Volume of blood to be drawn from each patient

Assessment		Sample volume (mL)	No. of samples	Total volume (mL)
Safety	Clinical chemistry	3.5	5	17.5
	Haematology	2	5	10
Pharmacokinetic (PK cohort only)		4	7	28
Total				55.5

## **7.2 Handling, storage and destruction of biological samples**

The samples will be used up after analyses as described here.

## **7.3 Labelling and shipment of biohazard samples**

The Principal Investigator ensures that samples are labelled and shipped in accordance with the Laboratory Manual.

## **7.4 Chain of custody of biological samples**

A full chain of custody is maintained for all samples throughout their lifecycle.

The Principal Investigator at each centre keeps full traceability of collected biological samples from the patients while in storage at the centre until shipment or disposal and keeps documentation of receipt of arrival.

The sample receiver keeps full traceability of the samples while in storage and during use until used or disposed of or until further shipment and keeps documentation of receipt of arrival.

AstraZeneca keeps oversight of the entire life cycle through internal procedures, monitoring of study sites and auditing of external laboratory providers.

## **7.5 Withdrawal of informed consent for donated biological samples**

If a patient withdraws consent to the use of donated biological samples, the samples will be disposed of/destroyed, and the action documented. If samples are already analysed, AstraZeneca is not obliged to destroy the results of this research.

The Principal Investigator:

- Ensures patients' withdrawal of informed consent to the use of donated samples is notified immediately to AstraZeneca
- Ensures that biological samples from that patient, if stored at the study site, are immediately identified, disposed of /destroyed, and the action documented
- Ensures the laboratory(ies) holding the samples is/are informed about the withdrawn consent immediately and that samples are disposed/destroyed, the action documented and the signed document returned to the study site
- Ensures that the patient and AstraZeneca are informed about the sample disposal.

AstraZeneca ensures the laboratory(ies) holding the samples is/are informed about the withdrawn consent immediately and that samples are disposed of/destroyed and the action documented and returned to the study site.

## **8. ETHICAL AND REGULATORY REQUIREMENTS**

### **8.1 Ethical conduct of the study**

The study will be performed in accordance with ethical principles that have their origin in the Declaration of Helsinki and are consistent with ICH/Good Clinical Practice, applicable regulatory requirements and the AstraZeneca policy on Bioethics and Human Biological Samples.

### **8.2 Patient data protection**

The Informed Consent Form (ICF) will incorporate (or, in some cases, be accompanied by a separate document incorporating) wording that complies with relevant data protection and privacy legislation.

### **8.3 Ethics and regulatory review**

An Ethics Committee (EC) should approve the final study protocol, including the final version of the Informed Consent Form and any other written information and/or materials to be

provided to the patients. The investigator will ensure the distribution of these documents to the applicable Ethics Committee, and to the study site staff.

The opinion of the Ethics Committee should be given in writing. The investigator should submit the written approval to AstraZeneca before enrolment of any patient into the study.

The Ethics Committee should approve all advertising used to recruit patients for the study.

AstraZeneca should approve any modifications to the Informed Consent Form that are needed to meet local requirements.

If required by local regulations, the protocol should be re-approved by the Ethics Committee annually.

Before enrolment of any patient into the study, the final study protocol, including the final version of the Informed Consent Form, is approved by the national regulatory authority or a notification to the national regulatory authority is done, according to local regulations.

AstraZeneca will handle the distribution of any of these documents to the national regulatory authorities.

AstraZeneca will provide Regulatory Authorities, Ethics Committees and Principal Investigators with safety updates/reports according to local requirements, including SUSARs (Suspected Unexpected Serious Adverse Reactions), where relevant.

## **8.4 Informed consent**

The Principal Investigator(s) at each centre will:

- Ensure each patient is given full and adequate oral and written information about the nature, purpose, possible risk and benefit of the study
- Ensure each patient is notified that they are free to discontinue from the study at any time
- Ensure that each patient is given the opportunity to ask questions and allowed time to consider the information provided
- Ensure each patient provides signed and dated informed consent before conducting any procedure specifically for the study
- Ensure the original, signed Informed Consent Form(s) is/are stored in the Investigator's Study File
- Ensure a copy of the signed Informed Consent Form is given to the patient

- Ensure that any incentives for patients who participate in the study as well as any provisions for patients harmed as a consequence of study participation are described in the informed consent form that is approved by an Ethics Committee.

## **8.5 Changes to the protocol and informed consent form**

Study procedures will not be changed without the mutual agreement of the Principal Investigator and AstraZeneca.

If there are any substantial changes to the study protocol, then these changes will be documented in a study protocol amendment and where required in a new version of the study protocol (Revised Clinical Study Protocol).

The amendment is to be approved by the relevant Ethics Committee and if applicable, also the national regulatory authority approval, before implementation. Local requirements are to be followed for revised protocols.

AstraZeneca will distribute any subsequent amendments and new versions of the protocol to each Principal Investigator(s). For distribution to Ethics Committee see Section 8.3.

If a protocol amendment requires a change to a centre's Informed Consent Form, AstraZeneca and the centre's Ethics Committee are to approve the revised Informed Consent Form before the revised form is used.

If local regulations require, any administrative change will be communicated to or approved by each Ethics Committee.

## **8.6 Audits and inspections**

Authorised representatives of AstraZeneca, a regulatory authority, or an Ethics Committee may perform audits or inspections at the centre, including source data verification. The purpose of an audit or inspection is to systematically and independently examine all study-related activities and documents, to determine whether these activities were conducted, and data were recorded, analysed, and accurately reported according to the protocol, Good Clinical Practice (GCP), guidelines of the International Conference on Harmonisation (ICH), and any applicable regulatory requirements. The investigator will contact AstraZeneca immediately if contacted by a regulatory agency about an inspection at the centre.

# **9. STUDY MANAGEMENT BY ASTRAZENECA**

## **9.1 Pre-study activities**

Before the first patient is entered into the study, it is necessary for a representative of AstraZeneca to visit the investigational study site to:

- Determine the adequacy of the facilities

- Determine availability of appropriate patients for the study
- Discuss with the investigator(s) (and other personnel involved with the study) their responsibilities with regard to protocol adherence, and the responsibilities of AstraZeneca or its representatives. This will be documented in a Clinical Study Agreement between AstraZeneca and the investigator.
- Discuss where the identification of data will be recorded eg, medical record(s), CRF and other associated documents. This will be documented in a Clinical Study Agreement.
- Discuss the specific requirements of the pharmacokinetic research part of the study with the investigator(s) (and other personnel involved with the study).

## **9.2 Training of study site personnel**

Before the first patient is entered into the study, an AstraZeneca representative will review and discuss the requirements of the Clinical Study Protocol and related documents with the investigational staff and also train them in any study specific procedures and the WBDC system utilised.

The Principal Investigator will ensure that appropriate training relevant to the study is given to all of these staff, and that any new information relevant to the performance of this study is forwarded to the staff involved.

The Principal Investigator will maintain a record of all individuals involved in the study (medical, nursing and other staff).

## **9.3 Monitoring of the study**

During the study, an AstraZeneca representative will have regular contacts with the study site, including visits to:

- Provide information and support to the investigator(s)
- Confirm that facilities remain acceptable
- Confirm that the investigational team is adhering to the protocol, that data are being accurately and timely recorded in the CRFs, that biological samples are handled in accordance with the Laboratory Manual and that study drug accountability checks are being performed
- Perform source data verification (a comparison of the data in the CRFs with the patient's medical records at the hospital or practice, and other records relevant to the study) including verification of informed consent of participating patients. This will require direct access to all original records for each patient (eg, clinic charts)

- Ensure withdrawal of informed consent to the use of the patient's biological samples is reported and biological samples are identified and disposed of/destroyed accordingly, and the action is documented, and reported to the patient.

The AstraZeneca representative will be available between visits if the investigator(s) or other staff at the centre needs information and advice about the study conduct.

### **9.3.1 Source data**

Refer to the Clinical Study Agreement for location of source data.

Source data refers to data generated as a result of the patient's inclusion in the study and includes all related medical examinations and other records.

## **9.4 Study agreements**

The Principal Investigator at each/the centre should comply with all the terms, conditions, and obligations of the Clinical Study Agreement, or equivalent, for this study. In the event of any inconsistency between this Clinical Study Protocol and the Clinical Study Agreement, the terms of Clinical Study Protocol shall prevail with respect to the conduct of the study and the treatment of patients and in all other respects, not relating to study conduct or treatment of patients, the terms of the Clinical Study Agreement shall prevail.

Agreements between AstraZeneca and the Principal Investigator should be in place before any study-related procedures can take place, or patients are enrolled.

### **9.4.1 Archiving of study documents**

The Investigator follows the principles outlined in the Clinical Study Agreement (CSA).

## **9.5 Study timetable and end of study**

The end of the study is defined as 'the last visit of the last patient undergoing the study'.

The study is expected to start in Q1 2011 and to end by Q4 2013.

The study may be terminated at individual centres if the study procedures are not being performed according to GCP, or if recruitment is slow. AstraZeneca may also terminate the entire study prematurely if concerns for safety arise within this study or in any other study with fulvestrant.

Study investigators will be notified by AstraZeneca when recruitment is complete.

## **10. DATA MANAGEMENT BY ASTRAZENECA OR DELEGATE**

Data management will be performed by Cognizant -AstraZeneca Data Management Centre.

Data will be entered in the Web Based Data Capture (WBDC) system at the study site. Trained study personnel will be responsible for entering data on the observations, tests and assessments specified in the protocol into the WBDC system. The eCRF Instructions will also guide the study site in performing data entry. Data entered in the WBDC system will be immediately saved to a central database and changes tracked to provide an audit trail. Site personnel will enter the data in the eCRFs.

The data will then be Source Data Verified (SDV), reviewed/ queried and updated as defined in the Data Management Plan. Quality control procedures will be applied to each stage of data handling to ensure that all data are reliable and have been processed correctly.

Adverse events and medical/surgical history will be classified according to the terminology of the latest version the Medical Dictionary for Regulatory Activities (MedDRA). Medications will be classified according to the AstraZeneca Drug Dictionary. All coding will be performed by the Medical Coding Team at the Cognizant-AstraZeneca Data Management Centre

The data collected through third party sources will be obtained and reconciled against study data.

When all data have been coded, validated, electronically signed and locked, clean file will be declared. Any treatment revealing data may thereafter be added and the final database will be locked.

## **11. EVALUATION AND CALCULATION OF VARIABLES BY ASTRAZENECA**

### **11.1 Calculation or derivation of efficacy variable(s)**

#### **11.1.1 Progression-Free Survival (PFS)**

PFS is defined as the time from randomisation to the time of the earliest objective disease progression (defined in Section 6.3.1), including death from any cause. Patients who have not progressed or died at the time of the data cut-off date or who have been lost to follow-up will be right-censored at the date of their last disease assessment.

For details of the primary statistical analysis of PFS see Section 12.

#### **11.1.2 Objective Response Rate (ORR)**

ORR is defined as the proportion of all treated patients with measurable disease at baseline who have a best objective tumour response of either CR or PR.

Confirmation of response is not required and therefore the following categories of best objective response will be derived:

CR: Single visit response of CR

- PR: Single visit response of PR
- SD : Stable disease recorded at least 8 weeks after the date of randomisation
- PD: Progression, or death in the absence of CR/PR or SD
- NE: No evidence of CR/PR or SD or PD or death (e.g. early censored patients)

### **11.1.3 Clinical Benefit Rate (CBR)**

CBR is defined as the proportion of patients in the FAS who have a best objective tumour response of CR, PR or SD  $\geq$  24 weeks. In the case of SD, follow-up measurements must have met the SD criteria at least once after study entry at a minimum interval of 8 weeks from the date of randomisation.

### **11.1.4 Duration of Response (DoR)**

Duration of response will be defined in two ways:

- (i) From date of first documentation of the response (CR or PR) until the date of disease progression or death from any cause.
- (ii) From date of randomisation until the date of disease progression or death in the absence of progression from any cause.

Any patient who has not progressed or died by the date of data cut-off, or who have been lost to follow up, will be right-censored in the analysis at the date of their last disease assessment.

### **11.1.5 Duration of Clinical Benefit (DoCB)**

Duration of clinical benefit will be defined as from date of randomisation until the date of disease progression or death from any cause, measured only in those patients who achieved a confirmed CR, PD or SD  $\geq$  24 weeks. DoCB should be in those patients with CB.

Any patients who has not progressed or died by the date of data cut-off, or who have been lost to follow up, will be right-censored in the analysis at the date of their last disease assessment.

## **11.2 Calculation or derivation of safety variable(s)**

Any new medical condition reported during the study will be recorded as an AE. Only those findings that are in addition to the condition being treated will be recorded as AEs (see Section 6.4.3 for recording of AEs). Conditions that are considered by the investigator to be unequivocally disease-related will not be recorded as AEs.

### **11.2.1 Other significant adverse events (OAE)**

During the evaluation of the AE data, an AstraZeneca medically qualified expert will review the list of AEs that were not reported as SAEs and DAEs. Based on the expert's judgement, significant adverse events of particular clinical importance may, after consultation with the

Global Patient Safety Physician, be considered OAEs and reported as such in the Clinical Study Report. A similar review of laboratory/vital signs/ECG data will be performed for identification of OAEs.

Examples of these are marked haematological and other laboratory abnormalities, and certain events that lead to intervention (other than those already classified as serious), dose reduction or significant additional treatment.

### **11.3 Calculation or derivation of patient reported outcome variables (Not Applicable)**

### **11.4 Calculation or derivation of pharmacokinetic variables**

The objectives of the PK analyses for this study are to derive parameters that describe the PK of fulvestrant 250 mg and 500 mg dosing regimens in Chinese patients and assess inter-individual and residual variability. The primary parameters to be reported are CL/F and Vss/F and derive secondary parameters Cmax, tmax, Cmin, AUC0-τ, and t1/2.

The concentration-time data from these studies will be analysed using a non-linear mixed effects model approach, a technique that is particularly useful for sparse data from a large number of individuals when the link between the individual parameters and the observed data are nonlinear. NONMEM will be used by the Clinical Pharmacology & DMPK group at AstraZeneca in addition to other supportive software such as R and Excel. Data from this study will be combined with data from studies 20 and 21 where further PK assessments will be undertaken.

The fixed effects describe the structural model or general form of the data. Random effects describe by the variation between individuals through individual specific regression parameters, which may be due to dependence on certain covariates and/or random but persistent variation. The residual error model captures random deviations between observed values and those predicted by the model. Model selection will be based on goodness of fit criteria including change of at least 6.64 (p=0.01) in the objective function value with 1 df, diagnostic plots, parameter, standard error and correlation estimates.

Secondary parameters will be derived for each individual from the final population model. Cmax, tmax, Cmin, and AUC0-τ will be derived following the 1st month of dosing and at steady-state. The table below details the calculation of the secondary PK parameters:

**Table 5 Calculation of secondary PK parameters**

Parameter	
t 1/2	Effective half-life: $\ln(2) \times (V_{ss}/F) / (CL/F)$
C max	The maximum individual predicted concentration in the central compartment (where the derivative approaches zero) in a standard dosing interval i.e. 28 days
t max	The time of C max

---

Parameter	
$C_{\min}$	The individual predicted concentration at the end of the dosing interval (actual time immediately prior to the next dose or 672 hours, if longer)
$AUC_{0-\tau}$	Integration of the area under the concentration-time curve from the time of dosing to the end of the dosing interval ( $\tau$ ) i.e. 28 days or less if the dose is administered a few days prior day 28

---

A summary of the results, table of parameters and plots demonstrating the fit of the model to the data for this study may be presented in the CSR. Full details of the pharmacokinetic analysis will be reported separately in the Pharmacokinetic Report.

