## LIST OF ABBREVIATIONS AND DEFINITION OF TERMS

The following abbreviations and special terms are used in this study Clinical Study Protocol.

Abbreviation or special term	Explanation
AE	Adverse event (see definition in Section 6.4.1)
AI	Aromatase inhibitor
ALP	Alkaline phosphatase
ALT	Alanine aminotransferase
ANC	Absolute Neutrophil Count
AO	Antioestrogen
ASA	Acetylsalicylic Acid (Aspirin)
Assessment	An observation made on a variable involving a patientive judgement (assessment)
AST	Aspartate aminotransferase
ATAC	Arimidex, Tamoxifen Alone or in Combination trial
AUC 0-τ	Area under the plasma concentration-time curve from the time of dosing to the end of the dosing interval
BP	Blood Pressure
CBR	Clinical Benefit Rate
CI	Confidence interval
CL/F	Apparent clearance
C max	Maximum plasma concentration of drug in a standard dosing interval
C min	Minimum plasma concentration of drug in a standard dosing interval
CR	Complete Response
CRA	Clinical Research Associate
CRF	Case Report Form (electronic/paper)
CSA	Clinical Study Agreement
CSR	Clinical Study Report
CT	Computed Tomography
CTCAE	Common Terminology Criteria for Adverse Event
DAE	Discontinuation of Investigational Product due to Adverse Event
DHEA	Dihydroepiandrosterone
DIC	Disseminated Intravascular Coagulation

Abbreviation or special term	Explanation
DoCB	Duration of Clinical Benefit
DoR	Duration of Response
EC	Ethics Committee, synonymous to Institutional Review Board (IRB) and Independent Ethics Committee (IEC)
ECG	Electrocardiogram
EDTA	Ethylene diamine tetra-acetic acid
Endpoint	A status of the patient that constitutes the ‘endpoint’ of a patient’s participation in a clinical study and that is used as the final outcome.
ER	Oestrogen Receptor
FAS	Full Analysis Set
FSH	Follicle Stimulating Hormone
GCP	Good Clinical Practice
GMP	Good Manufacturing Practice
HR	Hazard Ratio
HR	Heart Rate
HRT	Hormone Replacement therapy
i.m.	Intramuscular
ICF	Informed Consent Form
ICH	International Conference on Harmonisation
INR	International Normalisation Ratio
IP	Investigational Product
IS	Internal Standard
IVRS	Interactive Voice Response System
IWRS	Interactive Web Response System
LC-MS-MS	Liquid chromatography mass spectrometry method
LH-RH	Luteinising Hormone-Releasing Hormone
LMWH	Low Molecular Weight Heparin
LTED	Long-term oestrogen deprivation
Measurement	An observation made on a variable using a measurement device.

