f Laboratory assessments (haematology and biochemistry) will be performed before randomisation, before treatment (unless treatment is given within 7 days following screening assessments), at weeks 4 and 12, and every 12 weeks thereafter, until withdrawal from randomised treatment.

g within the 4 weeks before treatment

h Treatment continues to be given every 28 (± 3) days

i Patients must have a bone scan within 8 weeks before treatment or a skeletal survey within 4 weeks before treatment. Any hotspots identified on the bone scan must be confirmed by X-ray, computerized tomography (CT) scan or magnetic resonance imaging (MRI), within 4 weeks prior to treatment.

j All patients with metastatic bone lesions at baseline, must have bone scans or skeletal surveys every 12 weeks (+/- 2 weeks) until progression. Additional bone scans or skeletal surveys should be performed if clinically indicated. Abnormalities found on subsequent bone scans must also be confirmed by X-ray, CT scan, or MRI.

k Height is only captured at Visit 1.

l Pharmacokinetic samples will be collected from a cohort of 60 patients in total. Samples will be taken at day 1, day 15, day 29, day 57 and day 85 just prior to the randomised treatment injections. Two additional samples will also be taken at any time between day 5-10 and between day 33-38.

m A sample will be taken at the treatment discontinuation visit if this occurs before week 12.

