### **12.3 Determination of sample size**

The study will randomised 220 postmenopausal women with oestrogen receptor positive advanced breast cancer and it is expected to obtain at least 100 evaluable postmenopausal women per treatment group so as to meet the SFDA's requirements for registration trials. The 220 patients will be randomised in a 1:1 ratio to fulvestrant 500mg and fulvestrant 250mg. The primary analysis for PFS will be carried out when at least 150 progression events have been observed.

A criterion has been predefined for declaring consistency with CONFIRM. The results of this study would be considered to be consistent with CONFIRM if the hazard ratio point estimate for the treatment comparison is <1 (i.e. if it is in the same direction as in CONFIRM). With a

sample size of 220 randomised patients and 150 progression events, if there is no ethnic difference with the CONFIRM population, there is an 89% chance the HR <1.

For the PK part, no specific statistical hypothesis will be tested. Because of the long apparent  $t_{1/2}$ , intensive sampling for fulvestrant is problematic. For this reason sparse sampling is preferred and has been used in other fulvestrant PK studies ([Pritchard KI et al 2010](#); [Ohno.S et al 2010](#)). The sparse data will be analyzed by a mixed effect compartmental model (not non-compartmental analysis). Based on experience from prior fulvestrant PK studies, this study plans to recruit approximately 30 patients per arm for PK analysis for comparison with existing PK data for fulvestrant. Recruitment into the PK analysis will be on the basis of the first 30 patients per group who consent to the analysis.

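### Table 5 ends the dosing interval at the later of two times for Cmin but at the earlier for AUC0-τ, so after a permitted early injection the literal trough is read after the next dose

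*Protocol*

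**What the plan says.** Describing the pharmacokinetics of the two regimens is the first secondary objective (Protocol Section 2.2). Section 11.4 derives Cmin and AUC0-τ from the fitted model: "Secondary parameters will be derived for each individual from the final population model". They are wanted at two points, and "will be derived following the 1st month of dosing and at steady-state".

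Table 5 of Section 11.4 then sets the derivation rules:

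- **Cmin** is the individual predicted concentration at the end of the dosing interval, timed at the "actual time immediately prior to the next dose or 672 hours, if longer".
- **AUC0-τ** runs from dosing to the end of the dosing interval, given as "28 days or less if the dose is administered a few days prior day 28".
- **Cmax** is the maximum "in a standard dosing interval i.e. 28 days".

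The list of abbreviations describes Cmin as the "Minimum plasma concentration of drug in a standard dosing interval". On timing, footnote h of the study plan (Table 1) states: "Treatment continues to be given every 28 (± 3) days". Sections 3.1 and 5.5.2 give the same window. Section 12.3 adds: "For the PK part, no specific statistical hypothesis will be tested".

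**The concern.** The Cmin and AUC0-τ rows are adjacent and describe the same interval, but they end it by opposite rules. In the Cmin row, an actual time or 672 h, if longer, ordinarily means that the longer one is used. In the AUC0-τ row an early dose shortens the interval. With a ±3-day window, early doses are within protocol, so the conflict can arise in ordinary conduct.

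For an early-dosed patient the literal Cmin time falls after the next injection. That contradicts the row's own statement that the value belongs just before that injection and at the end of the interval. The reported trough would then be either a concentration on the rise after a new dose or, if the new dose is left out of the prediction, a value at a time that the patient never reached as a trough. Her Cmin and AUC0-τ would also refer to intervals of different length.

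At stake is the accuracy of one derived parameter in the pharmacokinetic description of the two regimens.

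**Working it through.** **Inputs from the protocol.** Standard interval 28 days, written as 672 h (Table 5). Permitted spacing 28 ± 3 days, so 25 to 31 days (Table 1 footnote h; Sections 3.1 and 5.5.2).

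**Step 1: reproduce the plan's figure.** 28 × 24 = 672 h, as stated. The window is 25 × 24 = 600 h to 31 × 24 = 744 h.

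**Step 2: apply both rows literally.** Let t be the time of the next dose, counted from the previous one. The Cmin time is max(t, 672). The AUC0-τ end is min(t, 672).

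| Next dose (days after last) | t (h) | Literal Cmin time (h) | Hours after next dose | AUC0-τ end (h) | Gap (h) |
|---|---|---|---|---|---|
| 25 | 600 | 672 | 72 | 600 | 72 |
| 26 | 624 | 672 | 48 | 624 | 48 |
| 27 | 648 | 672 | 24 | 648 | 24 |
| 28 | 672 | 672 | 0 | 672 | 0 |
| 29 | 696 | 696 | 0 | 672 | 24 |
| 30 | 720 | 720 | 0 | 672 | 48 |
| 31 | 744 | 744 | 0 | 672 | 72 |

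The rows agree only at exactly 28 days. For late doses the Cmin is still a pre-dose value, but it lies outside the interval used for AUC0-τ.

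**Step 3: illustrate the size.** The protocol gives no half-life or absorption values, so these are assumed: a one-compartment model with first-order input, terminal half-life 20, 40 or 60 days, single-dose peak at 5, 7 or 10 days, and 30 earlier doses 28 days apart. The single-dose concentration is proportional to exp(−k₁t) − exp(−k₂t), where k₁ = ln 2 / terminal half-life and k₂ is set to give the assumed peak time. Doses are added by superposition. The reference is the prediction just before the early dose.

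- *Next dose included, 1 day early (27 days):* the value at 672 h is 10% to 63% above the pre-dose value.
- *Next dose included, 3 days early (25 days):* 19% to 99% above.
- *Middle case (half-life 40 days, peak 7 days):* +21% at 1 day early and +38% at 3 days early.
- *Next dose left out:* the concentration simply goes on falling. The factor is close to exp(−ln 2 × 1/60) = 0.99 at the mild end (1 day early, half-life 60 days) and exp(−ln 2 × 3/20) = 0.90 at the other (3 days early, half-life 20 days). That is about 1% to 10% too low.

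A second set of assumptions (half-life 20 to 50 days, absorption half-life 1 to 4 days, next dose at 25 days) gives ratios of about 1.1 to 2.1. The direction of each error is the same in every case tried; its size depends on the assumed kinetics.

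**Step 4: apply one common end.** With min(t, 672) in both rows, Cmin is read at 600, 624, 648 and 672 h for next doses at 25 to 28 days, and at 672 h for 29 to 31 days. It is never read after the next dose and always matches AUC0-τ.

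**The case against.** The strongest reply is that the Cmin clause was meant as a cap: use 672 h if the actual interval is longer than that. This gives the earlier of the two times and agrees with the AUC0-τ row, the 28-day interval in the Cmax row and the abbreviation list. It also fits the row's opening words better. This reading is possible, and the fault may be no more than a drafting slip. But it is not the natural sense of the phrase, and a rule that supports two opposite times should not be left to the analyst.

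Second, a modeller could predict steady state under exact 28-day dosing, and the discrepancy would vanish. With sampling ending at day 85 (Section 6.6.1) that is plausible. The protocol does not say so, however, and the AUC0-τ row refers to actual early dosing.

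Third, the percentages need the literal reading, an early injection, a choice about the next dose, and kinetics from outside the protocol. That stands: they are illustrations.

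Two stronger inferences are tempting, and the documents do not support them.

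- *That the cap reading breaks down in month 1, because the next active 500 mg dose is on day 15.* Table 5 works with a 28-day interval, Section 3.1 treats day 15 as an additional dose inside the first month, and the early-dose exception covers only a dose shortly before day 28. Nothing ends an interval at day 15.
- *That a first-month tmax after day 15 in the 500 mg arm is wrong.* It describes the regimen as given, and describing the regimens is the stated aim.

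Nor do the documents show that a false ethnic difference would follow. Section 12.3 plans a comparison with existing pharmacokinetic data but does not single out Cmin, and how those data were derived cannot be seen here.

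**Conclusion.** The point holds as an inconsistency in a stated derivation rule. On the ordinary reading, Cmin and AUC0-τ end the same interval 24 to 72 h apart whenever the next dose is 1 to 3 days early or late. With an early dose, Cmin is timed after the injection it is meant to precede. These times are exact and rest only on protocol figures.

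The effect on the reported trough after an early dose is illustrative: about +10% to +99% if the next dose is in the prediction, about −1% to −10% if it is not, and nil under the cap reading or nominal 28-day prediction. How many intervals would be affected cannot be told from the protocol.

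The consequence is limited. Cmin is a derived parameter in a planned cohort of about 60 patients, Section 12.2.2 says only that it may be summarised, and no hypothesis is tested on it. CL/F and Vss/F, the primary pharmacokinetic parameters, and the PFS analysis are unaffected.

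**What to change.** In Table 5, give Cmin and AUC0-τ one interval end. The simplest change is to replace the last two words of the Cmin clause with *whichever is earlier*, so that Cmin is the predicted concentration just before the next dose or at 672 h, whichever comes first. The AUC0-τ row can stay as it is. Add a sentence stating that the first-month interval is the 28-day interval ending before the day-29 injection in both arms.

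This alters derivation wording only. The parameters are model predictions, so it needs no extra samples or patients and leaves the dosing schedule alone. It should be settled before the pharmacokinetic parameters are derived.
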